#### 11.5 Analysis of Dose Escalation Part

#### 11.5.1 Primary Objectives

The primary objectives are to:

- Determine the RP2D
- Establish the safety profile of GEN1044

# 11.5.2 Primary Endpoint – Dose Limiting Toxicities

The number of DLTs during the DLT period will be observed, as part of determining the RP2D.

The number treated per FAS, number of DLT evaluable subjects, number of DLTs, and DLT rate on each DL cohort will be tabulated.

#### 11.5.3 Primary Endpoint – Adverse Events and Safety Laboratory Parameters

#### 11.5.3.1 Analysis Set and Grouping for the Analyses

For all safety analyses, the FAS (which is identical to Safety Set) will be used.

The overall observation period will be divided into 3 mutually exclusive segments:

- 1. Pre-treatment period: from day of subject's informed consent to the day before first dose of trial medication
- 2. On-treatment period: from day of first dose of trial medication to 30 days after last dose of trial medication
- 3. Post-treatment period: starts when the on-treatment period ends.

#### 11.5.3.2 Adverse Events

Summary tables for AEs will include only AEs that started or pre-existing AEs that worsened during the on-treatment period, ie, the treatment-emergent adverse events (TEAEs).

The incidence of TEAEs (new or worsening from baseline) will be summarized by system organ class and/or preferred term; intensity (based on grades of NCI-CTCAE version 5.0) for all TEAEs except for CRS (see Section 10.4.1) and for ICANS (see Section 10.4.2); type of TEAE; relationship to trial treatment.

SAEs, non-serious TEAEs, and AESIs during the on-treatment period will be tabulated.

All fatal TEAEs, and all deaths (both on-treatment and post-treatment deaths) will be summarized.

Version: 4.0

All TEAEs, deaths, and SAEs (including those from the pre- and post-treatment periods) will be listed and those collected during the pre-treatment and post-treatment period will be flagged.

Further summaries of TEAEs and AESIs will be specified in the SAP.

#### 11.5.3.3 Laboratory Abnormalities

Grading of laboratory values will be assigned as per NCI-CTCAE version 5.0; further details will be provided in the SAP. The calculation of CTCAE grades will be based on the observed laboratory values only, clinical assessments will not be taken into account.

CTCAE grade 0 will be assigned for all non-missing values not graded as 1 or higher.

For laboratory tests where grades are not defined by the CTCAE, results will be categorized as low/normal/high based on laboratory normal ranges.

The following summaries will be generated separately for hematology, and biochemistry tests:

• Listing of all laboratory data with values flagged to show the corresponding CTCAE grades, if applicable, and the classifications relative to the laboratory normal ranges.

For laboratory tests where grades are defined by the CTCAE:

- Worst post-baseline CTCAE grade (regardless of the baseline status). Each subject will be counted only once for the worst grade observed post-baseline.
- Shift tables using CTCAE grades to compare baseline to the worst on-treatment value.

For laboratory tests where grades are not defined by the CTCAE:

• Shift tables using the low/normal/high/(low and high) (or other project-specific) classification to compare baseline to the worst on-treatment value.

#### 11.5.4 Statistical Hypothesis, Model, and Method of Analysis

No formal statistical hypotheses are formulated in this trial. Any P-values will be considered as hypothesis-generating results to be considered for future trials.

#### 11.5.5 Handling of Missing Values/Censoring/Discontinuations

The constraints of the DLT assessments is described in Section 4.2.2.

Imputation of missing or partially missing dates relating to adverse events will be detailed in the SAP.

Missing concentrations of laboratory parameters will be reported as is in data listings. Concentration values below the lower limit of quantitation (LLOQ, BLLOQ) will be handled as LLOQ/2 in summary statistics, and reported as is in data listings.

# 11.5.6 Supportive and Sensitivity Analyses

Not applicable.

# 11.5.7 Secondary Objectives

The secondary objectives are to:

• Establish the PK profile

Version: 4.0

- Evaluate immunogenicity of GEN1044, based on ADA response
- Evaluate anti-tumor activity (reduction in tumor size) based on response criteria relevant to the tumor type: ORR, DCR, DOR, and TTR.

#### 11.5.8 Secondary Endpoint – Pharmacokinetics

The PAS will be used for the analyses presented in this section.

Individual curves of concentration of GEN1044, including information on actual dose, will be presented for all subjects. All available data will be shown in these figures. The following PK parameters may be calculated based on the availability of data using non-compartmental methods:

- clearance;
- volume of distribution;
- maximum (peak) observed serum drug concentration (Cmax);
- time to reach maximum (peak) serum drug concentration (Tmax);
- area under the concentration-time curve (AUC) from time zero to last quantifiable sample (AUClast) and from time zero to infinity (AUCinf);
- time to reach maximum (peak) serum drug concentration (Tmax);
- predose trough concentrations (CTrough); and
- elimination half-life  $(T_{1/2})$ .

If deemed applicable, compartmental modelling approaches to parameter estimation will be applied.

Descriptive statistics of PK endpoints will include arithmetic and geometric means, standard deviation, CV%, median, minimum and maximum.

# 11.5.8.1 Data Handling Principles

Missing concentration values will be reported as is in data listings. Concentration values that are BLLOQ will be handled as LLOQ/2 in summary statistics, and reported as is in data listings. Any missing PK parameter data will not be imputed.

#### 11.5.9 Secondary Endpoint – Immunogenicity

The IAS will be used for the analyses presented in this section.

Titers of GEN1044 will be listed and positive/negative host immune response to GEN1044 and the presence of neutralizing antibodies (if assessed) will be summarized (positive/negative). The presence of PK concentrations above a certain threshold that depends on the drug tolerance of the ADA assay, at the same time as the ADA sample, may make the ADA undetectable and hence render non-conclusive. The association between positive/non-positive ADA and PK (predose, AUC,  $C_{max}$ ), major safety signals (such as  $CTCAE \ge grade 3$ ) and efficacy information (eg, change in tumor size by CT scan or MRI) will be explored, if possible.

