# 8.1.1 Treatment Discontinuation and Safety Follow-up Visit

The treatment discontinuation visit should be performed as soon as possible after permanent discontinuation of trial treatment, and will include the assessments described in Table 1 (Dose Escalation) and Table 5 (Expansion).

The Safety Follow-up visit (SFU) should be performed 30 (+14 days) after the subject has received the last dose of trial treatment.

If the treatment discontinuation visit is completed  $\geq 30$  days after last dose (eg, if dosing has been on hold awaiting resolution on safety issues, as described in Section 7), then the discontinuation visit and Safety Follow-up visit can be merged and completed on the same day.

Data collected should be added to the AE eCRF and the concomitant medications eCRF.

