# 11.1.6 Immunogenicity Analysis Set

The immunogenicity analysis set (IAS) will include all subjects who receive at least 1 dose of trial drug, and have a baseline and at least 1 evaluable on-treatment ADA sample.

Version: 4.0

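### The plan gives non-conclusive ADA results no category; if they fall into non-positive, the ADA–PK comparison is biased toward lower exposure in positives and ADA incidence may be understated

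*Protocol*

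**What the plan says.** Protocol Section 11.5.9 covers immunogenicity in a few sentences.

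- The summary is of "positive/negative host immune response to GEN1044", a two-way classification.
- Interference is acknowledged: "PK concentrations above a certain threshold that depends on the drug tolerance of the ADA assay", when present at the time of the ADA sample, "may make the ADA undetectable and hence render non-conclusive". The threshold is not given.
- The next sentence changes the vocabulary from negative to non-positive. It says that "The association between positive/non-positive ADA and PK" (predose, AUC, Cmax), together with major safety signals and efficacy information, "will be explored, if possible".

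No sentence says which group a non-conclusive subject joins, whether such subjects are in the incidence denominator, or how several samples from one subject combine. Section 11.6.11 carries the same method into the Expansion part.

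The immunogenicity analysis set (Section 11.1.6) takes treated subjects who "have a baseline and at least 1 evaluable on-treatment ADA sample". The word evaluable is not defined.

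Table 2 schedules ADA samples before infusion on C1D1, C2D1, C3D1, C5D1 and C7D1, then every fourth cycle, and at treatment discontinuation and safety follow-up (SFU). The SAP lists ADA response as the endpoint of a secondary objective (its Table 2), but defines no immunogenicity set and has no ADA or PK analysis section.

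**The concern.** Suppose non-positive means everyone who is not positive. It then mixes true negatives with subjects whose drug level was too high for ADA to be seen, while a positive can be recorded only below the tolerance limit. The grouping variable is partly defined by drug concentration, and drug concentration is the outcome being compared. The error has one direction: ADA appears to reduce exposure.

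The same grouping feeds the planned ADA–safety and ADA–efficacy comparisons. The positive/negative summary reports a named secondary endpoint, so a diluted incidence would also matter.

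The schedule makes interference plausible. Dosing is weekly through Cycle 4, so the C2D1, C3D1 and C5D1 samples are each planned 7 days after a dose. C7D1 is the first ADA sample planned after a 21-day interval. The full doses in SAP Table 1 run from 3 to 60 mg, so interference could also differ by cohort.

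**Working it through.** The documents give no ADA incidence, tolerance limit, PK variability or share of non-conclusive results, so there is no planned figure to reproduce. The check asks what the pooled grouping would show if ADA had **no** effect on PK.

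**Assumed inputs, none from the documents:** true incidence π = 10–40%; log-normal predose concentration with CV 30–80%; share above tolerance q = 10–50%; one sample per subject; every sample above tolerance non-conclusive; ADA independent of concentration.

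**Formulas.** With σ = √ln(1+CV²) and z the (1−q) normal quantile:

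- mean log concentration of positives, relative to all subjects: −σφ(z)/(1−q)
- apparent incidence if non-conclusive counts as negative: π(1−q)
- geometric mean ratio, positive to non-positive: exp{ −σφ(z) / [(1−q)(1−π(1−q))] }

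**Worked case** (π = 0.20, CV 50%, q = 0.30). σ = √ln 1.25 = 0.472, z = 0.524, φ(z) = 0.348. The mean for positives is −0.472 × 0.348 / 0.70 = −0.235. Apparent incidence is 0.20 × 0.70 = 14%. The ratio is exp(−0.235 / 0.86) = 0.76.

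**Results at π = 20%, CV 50%** (formula and simulation of 2,000,000 subjects per scenario agree; the AUC row is from simulation and assumes a correlation of 0.7 between log AUC and log predose):

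| Share non-conclusive | 0% | 10% | 30% | 50% |
|---|---|---|---|---|
| Predose ratio, positive / non-positive | 1.00 | 0.89 | 0.76 | 0.66 |
| AUC ratio | 1.00 | 0.92 | 0.83 | 0.75 |
| Apparent incidence (true 20%) | 20% | 18% | 14% | 10% |
| Predose ratio, positive / conclusive negative | 1.00 | 1.00 | 1.00 | 1.00 |

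Across all the assumed inputs with 10–50% non-conclusive, the predose ratio runs from 0.94 to 0.50. Pooling full doses from 3 to 60 mg (assumed dose-proportional, assumed cohort mix) gives 0.81, 0.57 and 0.38 for 10%, 30% and 50%.

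**Repeated samples.** If later low-drug samples resolve 50%, 90% or 100% of the non-conclusive subjects in the worked case, the ratio becomes 0.89, 0.98 or 1.00, and incidence 17%, 19% or 20%. A second check used π = 30%, CV 50%, 3–5 samples with intraclass correlation 0.5–0.8, and called a subject positive if any sample was detectable:

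| Samples above tolerance | Ratio, one sample | Ratio, 3–5 samples | Incidence, one sample | Incidence, 3–5 samples |
|---|---|---|---|---|
| 25% | 0.77 | 0.86–0.96 | 22.5% | 26–29% |
| 50% | 0.64 | 0.74–0.87 | 15% | 20–25% |

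**Does restricting to conclusive subjects solve it?** Only under no effect. Let ADA truly halve concentration (ratio 0.50), with π = 30%, CV 50% and one sample:

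| Share non-conclusive | 25% | 50% | 75% |
|---|---|---|---|
| Ratio, positive / conclusive negative | 0.63 | 0.73 | 0.83 |
| Incidence, conclusive subjects | 39% | 51% | 70% |
| Incidence, all subjects (row above × conclusive share) | 29% | 26% | 18% |

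Both groups are now cut off at the tolerance limit, so a true loss of exposure is attenuated. Incidence among conclusive subjects overshoots 30%, while incidence over all subjects falls short. Neither denominator is safe alone.

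**The case against.** The strongest reply is that the plan never assigns non-conclusive subjects to anything. Pooling them with negatives is inferred from the change of word from negative to non-positive straight after the interference sentence. A reader might go further and conclude that subjects certainly will be misclassified and that incidence is understated. The documents do not support that. The incidence summary names only positive and negative, a non-conclusive result is neither, and no denominator is stated. If evaluable in Section 11.1.6 means conclusive, subjects with only non-conclusive samples are outside the set and most of the dilution disappears. This part of the reply stands, so the conclusion must be conditional.

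A reader might also infer that subjects whose only conclusive sample is the SFU sample are dropped. Section 11.5.3.1 defines the "On-treatment period: from day of first dose of trial medication to 30 days after last dose of trial medication", while Section 8.1.1 says "The Safety Follow-up visit (SFU) should be performed 30 (+14 days) after the subject has received the last dose of trial treatment", so 14 of the 15 permitted days (31–44 out of 30–44) fall after the cut-off. That does not follow either. The period is set out under safety analyses and nothing ties it to the immunogenicity set. One earlier evaluable sample already qualifies a subject, and nothing removes the SFU sample of a subject already included. SAP Section 5.5 plans the 30th day after the last dose to coincide with the SFU visit. What remains is an undefined term.

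The comparison is also exploratory, no formal hypothesis is stated, enrolment has stopped, and the SAP serves an abbreviated report. This lowers the consequence. It does not remove the gap in a named secondary endpoint, and the SAP neither fills that gap nor says that the ADA analysis is dropped.

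**Conclusion.** The point holds conditionally. Section 11.5.9 recognises a third ADA state, defined by high drug level, and gives it no category. Its only wording for the PK comparison most naturally places that state with the negatives. Followed that way, the comparison leans toward lower exposure in ADA-positive subjects even with no ADA effect. Incidence becomes (1 − share non-conclusive) × true incidence if the same subjects count as negative and ADA does not alter drug level.

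The direction under no effect is certain on that reading; the size is not. The ratios rest on assumed incidence, variability and interference, and the single-sample figures are close to a worst case. Repeated samples bring them nearer to 1, and the bias is zero if no subject remains non-conclusive after all samples. The tolerance limit and trough levels needed to narrow the range are not in the documents.

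**What to change.** In Section 11.5.9:

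- Classify each subject as positive, negative or non-conclusive. State the tolerance limit and the rule for combining repeated samples. Requiring every sample to be conclusive before calling a subject negative would set aside someone with one high trough and a clean later negative, so the rule needs thought.
- Report all three counts, with incidence over all subjects in the immunogenicity set and over conclusive subjects, because each can be biased.
- Replace positive versus non-positive with a display of PK, safety and efficacy for the three groups separately, within dose level. Note that positive versus conclusive negative is unbiased only under no ADA effect and attenuates a true one.

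In Section 11.1.6, define evaluable and state that treatment-discontinuation and SFU samples count.

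In the SAP, add this analysis and the immunogenicity set, or state that the ADA analysis is dropped from the abbreviated report.

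The cost is some wording, one or two extra table rows, and smaller groups. With small dose cohorts the display will be descriptive only. It does not remove the selection by drug level, but it makes that selection visible.

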#### 11.5.10 Secondary Endpoint – Evaluation of Anti-tumor Activity

#### 11.5.10.1 Objective Response Rate

The confirmed objective response rate (ORR) is defined as the proportion of subjects with best overall response (BOR) of confirmed CR or confirmed PR (ie, "responders"), as per local review

Version: 4.0

and according to RECIST v1.1 (Eisenhauer et al., 2009). Repeat imaging may be performed no less than 4 weeks after the criteria for CR or PR is met to confirm the initial response.

An assessment of stable disease (SD) requires at least 5 weeks from C1D1 to scan date.

The BOR will be summarized in conjunction with the ORR. The estimated rates and the exact 2-sided 95% CIs (using the Clopper-Pearson method) will be summarized. Individual subject data listings will be provided.

#### 11.5.10.2 Disease Control Rate

The disease control rate (DCR) is defined as the proportion of subjects with BOR of confirmed CR, confirmed PR, or SD as per local review and according to RECIST v1.1 (Eisenhauer et al., 2009).

The estimated DCR and the exact 2-sided 95% CIs (using the Clopper-Pearson method) will be summarized in conjunction with the ORR.

# 11.5.10.3 Duration of Response

Duration of response (DOR) only applies to subjects with a best overall response that is either confirmed CR or confirmed PR according to RECIST v1.1 based on tumor response data per local review. The start date is the date of first documented response of CR or PR (ie, the start date of response, not the date when response was confirmed), and the end date is defined as the date of the first documented progression or death due to any cause. Subjects continuing without progression or death due to underlying cancer will be censored at the date of their last adequate tumor assessment. In case of progression after  $\geq 2$  missed visits, censoring will be done at last adequate tumor assessment date.

DOR distribution will be estimated using the Kaplan-Meier method, and the survival curve, median and 95% CI of the median will be presented. If too few responders this analysis may be omitted. Individual subject data listings will be provided.

#### 11.5.10.4 Time to Response

Time to response (TTR) is defined as the time from the date of C1D1 to the first documented response of either confirmed CR or confirmed PR. Date of initial response is used, not date of confirmation. CR and PR are based on tumor response data as per local review and according to RECIST v1.1 (Eisenhauer et al., 2009).

The TTR calculations are restricted to those subjects in the FAS with a confirmed PR or CR. TTR will be summarized and listed.

#### 11.5.11 Supportive Analyses of Secondary Efficacy Objectives and Endpoints

Not applicable.

#### 11.5.12 Other Safety Data

#### 11.5.12.1 Vital signs

Data on vital signs will be tabulated and listed; notable values will be flagged.

Version: 4.0

#### 11.5.12.2 ECGs

12-lead ECGs including PR, QRS, QT, heart-rate-corrected QT intervals using Fridericia's correction (QTcF), and RR intervals will be obtained for each subject during the trial. ECG data will be read and interpreted centrally. Triplicate ECGs are planned for the Dose Escalation part.

Categorical analysis of QT/QTc interval data based on the number of subjects meeting or exceeding predefined limits in terms of absolute QT/QTc intervals or changes from baseline will be presented. In addition, a listing of these subjects will be produced (by cohort).

## 11.5.12.3 ECOG Performance Status

ECOG-PS will be summarized by visit and listed.

# 11.5.13 Supportive Analyses for Secondary Objectives

Not applicable.

#### 11.5.14 Tolerability

Not applicable.

### 11.5.15 Exploratory Objectives

## 11.5.16 Exploratory Endpoint – Biomarkers

The exploratory biomarker assessments are intended to evaluate potential pharmacodynamic markers, and to identify markers predictive of response or resistance to GEN1044. Since this clinical trial is not designed to address specific biomarkers-related statistical hypotheses, the analysis of these data should be viewed as exploratory and hypotheses generating. Analyses may include how the peripheral T-cell activation and proliferation and cytokine release distributes between the type of responder groups. Descriptive analysis will be performed, and further details for additional analyses will be defined in the SAP. Results from exploratory biomarker assessments may be documented in separate reports.

Biomarkers, including pharmacodynamic markers, may be listed, tabulated, and plotted when deemed appropriate. Analyses may be stratified by clinical covariates or molecular subgroups using the appropriate statistical methods (eg, non-parametric or parametric, analysis of covariance [ANCOVA], proportional hazards regression or Kaplan-Meier methods) depending on the endpoint and the hypotheses. Baseline biomarker levels, or changes in biomarker levels, may be assessed for correlation with tumor response and other clinical endpoints to identify responsive or resistant subgroups, as well as biomarkers or pathways attenuated following treatment with GEN1044.

Additional analyses that may be performed after the completion of the end-of-trial clinical trial report (CTR) will be documented in separate reports. These analyses may include but are not limited to the meta-analysis of data from this trial combined with data from other trials or the analysis of biomarkers generated from samples collected during the trial but analyzed after the database lock and completion of the CTR. These analyses will be described in an addendum of the SAP, or in a stand-alone analysis plan document, as appropriate.

Planned analyses are based on the availability of clinically valid assays and may be deferred if emerging trial data shows no likelihood of providing useful scientific information.

#### 11.5.17 Exploratory Endpoint – Anti-tumor Activity Based on iRECIST

Responses assigned using iRECIST (Seymour et al., 2017) have a prefix of "i" eg, "immune" complete response (iCR) or partial response (iPR), and unconfirmed progressive disease (iUPD) or confirmed progressive disease (iCPD) to differentiate them from responses assigned using RECIST v1.1. Similar nomenclature is used for immune stable disease (iSD), immune objective response rate (iORR), immune disease control rate (iDCR) and immune duration of response (iDOR).

The iRECIST endpoints are analyzed using the same statistical methodology and the results presented in the same way as for the corresponding RECIST v1.1 endpoints, eg, iORR should be analyzed and reported in the same way as ORR.

If too few responders are observed, this exploratory analysis may be omitted. iRECIST will not be evaluated in subjects with prostate cancer.

